7.6.6 Follow-up: Annual

Subjects will be seen 12 months post-op (\pm 42 days), 24 months post-op (\pm 42 days), and annually thereafter until the last implant attempt subject completes their 24 month post-op visit or determined lost to follow-up. Annual visits, after 24 months, will have a window of \pm 84 days. The main purpose of the these visits is to assess subjects for adverse events and collect the data required to calculate all outcome measures (ASES, Constant score, Age Adjusted Constant Score, SANE, EQ-5D, subject satisfaction, pain). The following data will be collected and reported in the database:

- Adverse event assessment
- Pain medications
- X-ray independent radiologist will utilize imaging to assess X-ray data (defined in Section 7.3)
- Subject Questionnaire
- ROM test
- Strength test

Subjects may be asked to return for additional visits after the study is completed, if deemed necessary.

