7.6.9 Follow-up: Unsuccessful Implant Attempt

Reason for the unsuccessful implant attempt will be documented on the surgical form. Subjects will be seen at 12 and 24 months to gather available safety information. These visits may occur over the phone if the subject is unable to attend in person. Subjects will be exited after the 24 month visit.

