7.7 Additional Data Collection

Subjects may call or visit the investigative site at times other than for required study visits. It is only required to notify Tornier if the visit or phone call is associated with an adverse event, revision, device explant, reoperation, device malfunction, subject death, or study exit. Data associated with these events must be documented and reported in the database on the associated eCRFs.

Revision and Device Explants

A revision is a procedure that adjusts or in any way modifies or removes any component of the original implant configuration, with or without replacement of a component, after the initial surgery. A revision may also include adjusting the position of the original configuration.

An explant is a revision that includes permanent removal of any system component. If a subject has a revision that includes an addition of a glenoid component (revision to TSA) the Pyrocarbon humeral head must be permanently explanted.

All explanted system components, including the Pyrocarbon HH devices and stems, must be returned to Tornier for analysis per the system retrieval and analysis protocol in Appendix 4.

Reoperation

A reoperation is any invasive procedure to the affected shoulder that does not include removal, modification or addition of any components to the original implant configuration (e.g., drainage of a hematoma at the surgical site). Subjects will not be considered a failure solely due to a reoperation and will follow their original follow-up schedule.

Device Malfunction

All failures and malfunctions of the implant system must be reported to Tornier as soon as possible. In the event of a system malfunction, every effort must be made to return the suspected system to Tornier for analysis.

Death

During the study, all deaths must be reported to the Sponsor within 10 working days of the study personnel's knowledge of the death. A copy of death records, medical records for the events that led to the subject's death, death certificate (if available) and an autopsy report (if performed) must be sent to the Sponsor as soon as they become available.

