7.8 Study Exit

Subjects will exit the study after the last subject with an implant attempt completes their 24 month followup visitor is determined lost to follow-up. Reasons for exiting a subject early may include:

- Subject voluntary withdraw of participation
- Investigators may withdraw subjects from the study if the investigator feels it is in the subject's best interest to withdraw or if the subject demonstrates non-compliance to the CIP.
- Death
- Subject lost to follow-up.
- It was determined that subject did not meeting inclusion/exclusion criteria prior to surgery (preoperative screen failure)

In the case that the subject is determined to be lost to follow-up, at least three documented attempts must be made to contact the subject and at least one of the attempts must be in writing via certified letter. Subjects who exit the study prior to study completion will not be replaced.

8 Investigational Device Handling and Traceability

The Ascend Flex System stems and associated instruments are not investigational and will not require tracking while at the investigative site. When the Pyrocarbon HH is paired with the Ascend Flex stem, and implanted in the body, the system (Pyrocarbon HH and Ascend Flex Stem) are both considered investigational and require tracking.

The Pyrocarbon HH is investigational and will be tracked from the time it is shipped from Tornier until it is either implanted into a study subject, or returned to Tornier after completion of the enrollment. A Device Accountability Log will be maintained at each study site and will be provided by Tornier in the Regulatory Binder. Devices allocated for investigational site use will be recorded in the Device Accountability Log upon delivery to the study site and will be stored in a secured area until use. No devices will be shipped to an investigative site until the site receives IRB approval to conduct the study. Each site will be responsible for tracking the receipt and disposition of all study devices. All unused study devices must be returned to Tornier.

The Device Accountability Log will be updated as devices are received, opened, used or returned. It will contain: receipt dates of devices and their lot or serial numbers; subject study identification number and their implant dates; and dates devices were returned to Tornier, along with the reason for the return.

9 Study Deviations

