10.1 Adverse Event Assessment Process

An adverse event (AE) assessment must be completed for each subject at every study visit. Ongoing AEs will be assessed at each study visit and the update reported to Tornier. If the AE is still unresolved at study exit, it must be updated to state "unresolved at study exit".

If the subject is treated by a health-care professional other than the investigator for treatment-related AEs, the investigator must request copies of the medical records and complete all required AE data collection. If the investigator is unable to obtain these medical records, efforts to obtain them should be documented in the subject's medical record.

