### 12.5. Primary Effectiveness Analysis

### 12.5.1. Primary analysis

The primary endpoint is the rate of patient success at 24 months. A subject is a success at 24 months if:

- Their change in Constant score is  $\geq 17$  and
- They did not have revision surgery; and
- There is no radiographic evidence of system disassembly or fracture, and
- They did not have a system-related serious adverse event.

Subjects that undergo revision surgery within 24 months will be considered a primary endpoint failure at the time any component of the system is revised.

If a subject is missing the 24 month radiographic evidence assessment or Constant score component of the composite endpoint and did not have a system-related SAE or revision surgery, they will be excluded from the primary analysis due to inability to claim success or failure.

Subjects in whom an implant was attempted but the implant was unsuccessful will be included as failures in the primary analysis, regardless of the availability of 24 month radiographic evidence assessment or Constant score.

The presence of radiographic evidence of system disassembly or fracture will be assessed by independent radiologists. Discrepancies among the independent evaluations will be settled by majority rule. If the radiologists are unable to assess or the image wasn't available at 24 months, this will be considered missing data and the subject will be excluded from the primary analysis.

The non-inferiority of the test system to the performance goal will be evaluated using the 95% CI for the observed test system success rate. The study will be considered a success if the lower bound of the confidence interval is greater than 75% (85% - 10%).

The number of subjects who are successes (X) for each of the 4 individual components of the composite success endpoint, along with the number evaluated (N), will be summarized at 12 and 24 months as (X/N) and displayed with the overall success endpoint results based on data up to 12 and 24 months.

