### 12.5.2. Sensitivity Analysis

Two separate sensitivity analyses will be completed on the primary endpoint, outlined below:

- 1) The primary effectiveness analysis will be repeated under the assumption that all subjects with missing endpoint data were successful.
- 2) The primary effectiveness analysis will be repeated under the assumption that all subjects with missing endpoint data were failures.
- 3) The primary effectiveness analysis will be repeated using multiple imputation for missing endpoint data. The covariates that may (list not all-inclusive) be included in the multiple imputation process are: age, gender, treated shoulder, arthritis diagnosis, Constant score (baseline and 12 month), and BMI.

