In the Aequalis historical control dataset, 10 of 191 subjects had a revision of some type within 24 months from surgery for an estimated revision rate of 5.2%. Using the same non-inferiority margin of 10%, a sample size of 100 is adequate to test with at least 90% power and a one-sided alpha of 0.025. Estimates for the revision rate at 24 months and an upper 97.5% confidence bound will be generated using a Kaplan-Meier time to event analysis. If this value is less than 13.2%, then the null hypothesis is rejected and it is concluded that the reivision rate is acceptable and not inferior to prior approved devices. Additional summaries

will include the proportion of subjects with a revision rate within 24 months along with a binomial two-sided 95% confidence limits.

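### The exit rules do not require revision status to be established for implanted subjects, so a revision done elsewhere that the site never hears of is left out of both the primary analysis and the revision-rate test

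*Protocol*

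**What the plan says.** **Loss and withdrawal.** For a subject lost to follow-up, Protocol 7.8 requires that "at least three documented attempts must be made to contact the subject and at least one of the attempts must be in writing", by certified letter. For voluntary or investigator-led withdrawal it sets no further step. In neither case does it ask whether the shoulder has been revised, or when it was last known not to have been.

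**Mode of visit.** For intra-operative screen failures (7.6.8) and unsuccessful implant attempts (7.6.9): "These visits may occur over the phone if the subject is unable to attend in person". For implanted subjects, 7.6.6 says "Subjects will be seen 12 months post-op" and gives no telephone option. Nor do 7.6.5, 7.6.10 or 7.6.11.

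**Events between visits.** On contacts outside the schedule, Protocol 7.7 says: "It is only required to notify Tornier if the visit or phone call is associated with an adverse event, revision, device explant". Where another professional treats a treatment-related event, Protocol 10.1 says that "the investigator must request copies of the medical records and complete all required AE data collection".

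**Primary analysis.** SAP 12.5.1 makes a revision within 24 months a failure. Subjects who lack the 24-month X-ray assessment or Constant score, and have no revision or system-related SAE, are handled differently: "they will be excluded from the primary analysis due to inability to claim success or failure". Protocol 13.2.4 and SAP 12.5.2 repeat the analysis "under the assumption that all subjects with missing endpoint data were failures", and also with all missing as successes and with multiple imputation.

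**Revision-rate test.** SAP 12.6: "Estimates for the revision rate at 24 months and an upper 97.5% confidence bound will be generated using a Kaplan-Meier time to event analysis"; the bound must fall below 13.2%. SAP 11.2, whose title mentions censoring, gives no censoring rule and removes early withdrawals from the analysis of secondary endpoints.

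**The concern.** Revision is both a component of the primary endpoint and a tested secondary endpoint. It can also be established without an in-person visit. A known revision counts as a failure; an unknown one in a subject without 24-month data removes the subject. The primary error therefore runs one way, taking a failure out of both the count of failures and the denominator. In the revision-rate test the event is not counted, whichever SAP section governs.

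The routes that could reveal an outside revision depend on the subject contacting or attending the site, or on the site already knowing of the treatment. A missed visit or an exit triggers none of them. The plan thus gives easier remote safety follow-up to subjects without the implant than to those who carry it.

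**Working it through.** **1. The plan's own figures.** Inputs from Protocol 13.2.2: null rate 0.75 (0.85 − 0.10), assumed rate 0.85, one-sided 0.025, power 80%, attrition 15%.

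n = [(1.960·√(0.75·0.25) + 0.842·√(0.85·0.15)) / 0.10]² = 132.07, so 133. Then 133/0.85 = 156.5, so 157. Both figures reproduce. The allowance for missing endpoint data is 157 − 133 = 24.

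**2. What happens to a revision done elsewhere.**

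| Situation | Primary analysis | Revision-rate test |
|---|---|---|
| Site learns of it (visit, call, records) | Failure | Event |
| Never learned of, 24-month data missing, SAP 12.6 read alone | Excluded | Presumably censored; not counted |
| Same, with early withdrawal, SAP 11.2 read literally | Excluded | Excluded; not counted |

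**3. Effect on the revision rate.** Followed subjects are taken at 5.2% (10/191, SAP 12.6). All 24 are taken as lost, which is an upper limit, with revision rate r assumed.

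True rate = (133 × 0.052 + 24r)/157

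| r | Hidden revisions (24r) | Total revisions | True rate |
|---|---|---|---|
| 10% | 2.4 | 9.3 | 5.9% |
| 15% | 3.6 | 10.5 | 6.7% |
| 20% | 4.8 | 11.7 | 7.5% |

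Rounding the last row up to 12/157, the exact upper 97.5% bound is 12.97%, below 13.2%. With everyone's status known, the test still passes.

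**4. When the revision-rate test could turn.** Assumptions: 24 of 157 lost evenly over 24 months, m of them revised soon after last contact, and the other lost subjects still censored at last contact. The SAP names no method for the Kaplan-Meier bound, so two are shown. With S the survival estimate and G the Greenwood sum:

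- linear: 1 − S + 1.96·S·√G
- log-log: 1 − S^exp(1.96·√G/|ln S|)

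| Recorded revisions | Estimate without hidden revisions | First failing m, log-log | First failing m, linear |
|---|---|---|---|
| 8 | 5.6% | 3 (13.25%) | 5 (13.5%) |
| 10 | 6.95% (bounds 12.6% log-log, 11.1% linear) | 1 (13.23%) | 3 (13.6%) |

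The two log-log figures lie almost on the limit, and a small change in assumed timing could move them across it. These reversals come at lower totals than step 3 suggests because the remaining lost subjects stay censored early, which reduces the numbers at risk.

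**5. When the primary result could turn.** The documents name no interval method; exact (Clopper-Pearson) and Wald lower bounds are shown against 75%. Added subjects are all failures.

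| Successes/N | Exact | Wald |
|---|---|---|
| 113/133 (planned rate) | 77.7% | 78.9% |
| 113/137 (4 added) | 75.06% | 76.1% |
| 113/139 (6 added) | 73.8% | 74.8% |
| 110/133 (exact pass boundary) | 75.2% | passes |
| 110/134 (1 added) | 74.5% | 75.6% |

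At the planned rate, reversal takes 5 hidden failures by the exact method or 6 by Wald. One suffices only at the boundary of the method in use.

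**6. How tight the planned bound is.** With 24 missing counted as failures, 113/157 = 72.0% has an exact lower bound of 64.3%. Passing would need 129/157 (exact lower bound 75.3%), that is, 129 successes among 133 evaluable subjects. At the full allowance this analysis is a wide bound. It cannot tell a revised subject from one who moved away.

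**The case against.** The strongest case against has five parts.

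- **The primary endpoint is protected.** The missing-as-failure analysis covers every undetected revision at once. This stands as a bound, but trial success rests on the analysis that excludes these subjects (SAP 8 and 12.5.1).
- **Capture is broader than one route.** Adverse events are assessed at every visit, X-rays are read independently, outside records must be requested, explanted components must be returned, and implanted subjects are seen annually beyond 24 months until the last subject finishes. This stands, and narrows the point to a subject revised after the last attended visit, who never returns, and whose site is never told.
- **The telephone difference has a reason.** Implanted subjects need X-ray, motion and strength measurements in person. That explains the full visit, but not the absence of a status-only call.
- **Contact attempts already do much of this.** A revision reported during a successful contact must be entered. True, but nothing requires the question to be put, and if contact fails only a records check would help.
- **Unseen material may ask for it.** The study-exit form and the Monitoring Plan are not in the documents. This remains possible.

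A reader might also infer that lost subjects are formally censored as unrevised. The SAP does not say so: censoring is inferred from the Kaplan-Meier method, and SAP 11.2 read literally excludes early withdrawals. A reader might likewise infer that dissatisfied subjects are the ones most often lost. That is plausible, but nothing in the documents supports it.

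**Conclusion.** The gap is real but narrow. It concerns implanted subjects revised elsewhere whose site never learns of it. In the primary analysis such a subject is excluded rather than failed, and the planned worst-case analysis bounds this without deciding success. In the revision-rate test the event is lost, no sensitivity analysis covers it, and SAP 11.2 and SAP 12.6 must be reconciled.

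The size cannot be determined from the documents. The 24 is an allowance for all missing endpoint data, including deaths, unreadable X-rays and missing Constant scores, not a forecast of loss to follow-up. The 10% to 20% revision rates in lost subjects and the timing in the Kaplan-Meier illustration are assumptions.

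Two stronger readings are not supported. One is that plausible loss would by itself overturn the revision-rate test: the 5.9% to 7.5% scenarios still pass when everyone's status is known. The other is that a single hidden revision overturns the primary result: that needs a result exactly on the boundary, and 110/134 still passes by Wald. A few hidden revisions matter only if a result is close to its threshold. The change is worth making because it is cheap and recovers outcome data that the plan as written could lose.

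**What to change.** **Protocol 7.6.6 and 7.8.** When an implanted subject misses the 12- or 24-month visit or exits early, record by telephone, letter or, where authorised, medical records whether the operated shoulder has been revised, the revision date if so, and the date last known unrevised. Allow a status-only telephone contact for this.

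**SAP 12.5.1.** Count a revision found this way within 24 months as a primary failure.

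**SAP 11.2 and 12.6.** Count it as an event in the revision-rate test. State that subjects without a known revision are censored at the date last known unrevised, not excluded. Add a worst-case or tipping-point sensitivity analysis to this test.

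**Cost.** A few protocol and SAP sentences, a few eCRF fields, one added analysis and slight extra site work; for lost subjects the contact attempts are already required. The sample size stays at 133 and 157. In the primary analysis the check can only move subjects from missing to failure, so the observed success rate may be slightly less favourable.

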10.1 Adverse Event Assessment Process

An adverse event (AE) assessment must be completed for each subject at every study visit. Ongoing AEs will be assessed at each study visit and the update reported to Tornier. If the AE is still unresolved at study exit, it must be updated to state "unresolved at study exit".

If the subject is treated by a health-care professional other than the investigator for treatment-related AEs, the investigator must request copies of the medical records and complete all required AE data collection. If the investigator is unable to obtain these medical records, efforts to obtain them should be documented in the subject's medical record.

10.2 Adverse Event Definitions

Adverse Event (AE): An Adverse Event is any unfavorable or unintended sign, symptom, condition or disease in a study subject, where the experience occurs during the course of the study; regardless of its relationship to the test product or surgical procedure.

An Adverse Event may be volunteered spontaneously by the subject or discovered as a result of questioning or by physical examination by the Investigator or clinical study, or recorded anywhere in the patient's medical record. An Adverse Event must be documented in the progress notes and on an AE eCRF.

For the purpose of this study, investigators are required to report all adverse events.

The relationship of the AE to the study system or the implant procedure will be determined by the investigator and reported on the eCRF. An independent physician consultant will review each reported AE for appropriate classification.

Device Related: An AE that results from the presence or performance of the device.

Procedure Related: An AE that occurs as a result of the implant procedure.

Definitions of Relatedness:

- **Definite**: A definite or certain association exists between the AE and the study device/system or implant procedure.
- **Possible**: The AE cannot be explained by other causes (underlying disease, concomitant medical or concurrent treatment) and is possible that the AE occurred as a result of the study device/system or implant procedure.
- Not related: The AE has no relationship with receipt of the study device or implant procedure, or it can be explained by other factors; including underlying disease, concomitant medication or concurrent treatment.

Unavoidable Adverse Events: those that are expected to occur and inherent with the surgical procedure. These only need to be reported if they are deemed by the investigator to be more serious in duration or intensity than expected. Unavoidable AEs include:

- Anesthesia related nausea/vomiting
- Low-grade fever for ~48 hours post-op
- Incisional pain for ~72 hours post-op
- Mild to moderate bruising or hematoma for ~ one week post-op
- Sleep problems (insomnia) for ~ 72 hours post-op
- Back pain related to lying on table

Normal incision redness

Serious Adverse Event (SAE)

An adverse event is serious when it:

- Led to death,
- Led to serious deterioration in the health of the subject, that either resulted in
 - A life threatening illness or injury, or
 - A permanent impairment of a body structure or a body function, or
 - In-patient or prolonged hospitalization, or
 - Medical or surgical intervention to prevent life-threatening illness or injury or permanent impairment to a body structure or a body function,
- Led to fetal distress, fetal death or a congenital abnormality or birth defect.

Unanticipated Adverse Device Effect (UADE)

Any serious adverse effect on health or safety, any life-threatening problem or death caused by, or associated with a device, if that effect, problem, or death was not previously identified in nature, severity, or degree of incidence in the study protocol or informed consent; or any other unanticipated serious problem associated with a device that relates to the rights, safety, or welfare of subjects.

Anticipated Adverse Events

The risks associated with the Pyrocarbon HH used with the Ascend Flex stems are listed below. The complications could cause inflammation, resulting in increased pain and the need for revision surgery.

- Dislocation
- Component loosening
- Component breakage
- Component wear
- Component migration
- Delayed wound healing
- Bone resorption
- Glenoid erosion
- Poor bone growth
- Over tension of the soft tissues
- Impingement of tendons or bursa in the shoulder from bones of the shoulder
- Rotator cuff tear
- Instability
- Stiffness
- Weakness
- Chronic postoperative pain/disability
- Nerve damage causing paralysis
- Tissue lesion
- Vascular Injury

- Infection or any other event that could follow surgery (pulmonary embolism, heart attack, etc.)
- Fracture below the humeral implant.
- Possible metal sensitivity
- Oversized or undersized humeral head (the "ball portion") could cause loss of mobility and pain.

